#### **4.13 Use of baseline values**

The staging results of RECIST tumor assessments including date of assessment, size(s) of target tumor(s), or number of metastases at baseline are used for PFS analysis.

#### **4.14 Use of covariates**

Not applicable.

#### **4.15 Identification of fixed and random factors**

Not applicable.

#### **4.16 Subset analyses**

No subgroup analyses are planned.

#### **4.17 Interim and follow-up analyses**

No interim analyses will be done due to the small number of participants. No follow-up analyses are planned.

#### **4.18 Study stopping rules**

The study may be discontinued at the discretion of the sponsor in any of the following events:

- Medical or ethical reasons affecting the continued performance of the study (e.g., recommendations of the DSMB in the above-mentioned special stopping rules after randomization of the first twenty patients and screening of the first fifty patients, respectively),
- Difficulties in the recruitment of patients,
- Inefficacy of the study treatment,
- Occurrence of AEs previously unknown in respect of their nature, severity, and duration or unexpected incidence of known AEs.

#### **4.19 Statistical significance levels**

Not applicable.

#### **4.20 Methods for handling dropouts and protocol violators**

Patients withdrawn from the study for reasons stated in section 3.3 will not be replaced.

For patients considered to be significantly noncompliant by the investigator or sponsor with the requirements of the protocol, i.e., protocol violations such as pregnancy, the treatment will be permanently discontinued. Other reasons for permanent treatment discontinuation for a patient include withdrawal criteria and:

- Three years of study treatment,
- Patient experiences PD,
- Patient experiences unacceptable toxicity or an adverse experience that would, in the investigator's or sponsor's judgment, make continued administration of the study regimen an unacceptable risk,
- Situations requiring a therapeutic intervention not permitted by the treatment plan,
- Development of an intercurrent illness or situation which would, in the judgement of the investigator, affect assessments of clinical status and study endpoints to a significant degree,
- Specific request of the sponsor.

Patients for whom the treatment is permanently discontinued will remain in the study unless withdrawal. All patients with permanent treatment discontinuation, except for withdrawal of informed consent, lost to follow-up, or death, will be followed up as planned.

#### **4.21 Methods for handling more than two treatment groups**

Not applicable.

#### **4.22 Methods for handling concomitant medications**

Concomitant medications will be listed in Listing 6.2. There will be no analysis of their impact on study treatment or outcome.

#### **4.23 Changes to the planned analyses**

Due to the small number of patients, most analyses are shown in listings. Not all study objectives can be considered.

## 5 Mock-ups for tables, listings, and figures

The following TLF are planned. The fields marked in checked grey (listings) and the grey text in curly braces (tables) show the programmer where the parameter to be analyzed may be found and will not appear in the report.

Regarding listings, alternative choices such as yes or no, male or female, and positive or negative will not be displayed, but units will be given as shown below. Furthermore, abbreviations listed in chapter 1 will be used for legibility.

### 5.1 Tables

**Table 1: General data**

Populations	[N, %]
Number of patients	xx (100.00)
Number of patients in analysis populations	
mITT=SP	
PP	
Number of patients in treatment arms	
A	
B	
Number of participating clinics	

**Table 2: Patients' first conversion to RAS wild-type**

	Time from baseline sampling until first detection of RASwt [days]								
	N	Mean	STD	Min	Q1	Median	Q3	Max	NMiss
A									
B									
Total									

**Table 3: Responses**

Responses according to RECIST v1.1 criteria including Overall response rate (ORR)	Arm A [N, %]	Arm B [N, %]	Total [N, %]
Number of randomized patients			
Most recent response			
Complete response (CR)			
Partial response (PR)			
Stable disease (SD)			
Progressive disease (PD)			
Best response			
Complete response (CR)			
Partial response (PR)			
Stable disease (SD)			
Progressive disease (PD)			
Overall response			
CR or PR (ORR)			

**(Optionally) Table 4.1: AEs - overview**

Overview	5-FU [N, %]	Folinic acid [N, %]	Irinotecan [N, %]	Cetuximab [N, %]	Total [N, %]
Number of patients in mITT					
Patients with any AE					
Patients with AEs by maximal grade					
Grade 1					
Grade 2					
Grade 3					
Grade 4					

Grade 5							
Number of AEs							
Patients with treatment-related AEs							
Number of treatment-related AEs							
Patients with any SAE							
Patients with SAEs by seriousness criteria							
Death							
Life-threatening							
Hospitalization							
Persistent or significant disability/incapacity							
Congenital anomaly/birth defect							
Important medical event							
Number of SAEs							
Patients with any special AE							
Patients with special AEs by speciality criteria							
Pregnancy							
Medication error							
Number of special AEs							
Patients with AEs leading to discontinuation							
Number of AEs leading to discontinuation							

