10.1.2 Secondary Variables

- OS, defined as time from date of randomization until death from any cause; OS should be censored, in patients without an OS event, on the last date they were known to be alive.
- TFTS, is defined as time from date of randomization to failure of treatment strategy defined as treatment discontinuation for any reason, including disease progression, withdrawal of consent, treatment toxicity, patient preference, loss to follow up or death from any cause.
- PFS rate 1 year after date of randomization, derived by Kaplan-Meier method (defined as the estimated rate of patients with progression or death from any cause 1 year after date of randomization)
- Depth of response (DpR) in terms of reduction of tumor mass in experimental and control arms, defined as the percentage of tumor shrinkage, based on longest diameters of all target lesions or reconstructed volume, observed at the lowest point (nadir) compared to baseline. The time for DpR assessment varies between patients relating to the individual achievement of maximal tumor shrinkage, which typically occurs 4–6 months after the start of 1st-line therapy. DpR varies between 100% (= all target tumor lesions have disappeared) and 0% (=no change in tumor size) and has a negative value in cases of increased tumor volume.
- Percentage of patients with metastasis resections, defined as percentage of patients with complete resection of primary tumor and metastases (R0-resection), at any time after the start of 1st line therapy until the end of the treatment strategy.
- ORR, defined as the proportion of randomized patients with CR or PR as best response since start of 1st line therapy.
- Safety, defined as all SAEs regardless of causality, and non-serious adverse events according to CTCAE Version 5.0 criteria, that are definitely, probably, or possibly related to the administration of any study treatment, or that cause permanent discontinuation of treatment, recorded from the date of signature of Informed Consent.

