### 3.2 Analysis populations

**Modified Intention to Treat (mITT):** All randomized patients who received at least 1 dose, complete or incomplete, of study medication.

**Safety population (SP)** = mITT population.

**Per protocol (PP) population:** All randomized patients who received study treatment according to randomization and did not have major disqualifying protocol violations, i.e., did not violate any selection criterion.

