#### Secondary objectives:

- OS in experimental and control arms from date of randomization,
- Time to failure of treatment strategy (TFTS) in experimental and control arms after randomization,
- PFS rate one year after date of randomization,
- Depth of response (DpR) in terms of reduction of tumor mass in experimental and control arms after of first-line treatment,
- Metastatic resections in experimental and control arms after first-line treatment,
- ORR defined as proportion of patients with partial response (PR) or complete response (CR) as best response in experimental and control arms after start of first-line treatment,
- Safety profile according to the National Cancer Institute's (NCI) Common Terminology Criteria of Adverse Events (CTCAE) version 5.0 criteria in experimental and control arms recorded from date of signature of informed consent.

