#### 4.3.9 Safety

Regarding the secondary objective safety, all adverse events (AEs) will be ordered by patient number and summarized in the following listings:

- Terminology and timeline of AE together with causality to study treatments as well as possible actions taken (Listing 28.1) and serious or special classification (Listing 28.2).

Optionally, if the number of AEs is sufficient, then the AEs will be analyzed in frequency tables including number of treatment-related AEs, number of AEs that cause permanent treatment discontinuation, system organ class (SOC) and preferred terms (PT) according to the Medical Dictionary for Regulatory Activities (MedDRA). The following tables will optionally be added:

- An AE overview (Table 4.1), number of AEs with respect to MedDRA grouping and NCI CTCAE grading (Table 4.2), and number of patients with AE by maximal grade with respect to MedDRA coding.

SAEs are classified as special if they involve pregnancy or medication error.

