**(Optionally) Table 4.2: AEs - System Organ Class (SOC) and Preferred Term (PT) by NCI CTCAE grade**

SOC	PT	NCI CTCAE grade					Total	
		1	2	3	4	5	N	%
Number of AEs								100

SOC1								
	PT11							
	PT12							
	...							
SOC2								
	PT21							
	PT22							
	...							
...								

**(Optionally) Table 4.3: AEs - number of patients with respect to System Organ Class (SOC) and Preferred Term (PT) by maximal NCI CTCAE grade**

SOC	PT	Maximal NCI CTCAE grade					Total	
		1	2	3	4	5	N	%
Number of patients with any AE								100
SOC1								
	PT11							
	PT12							
	...							
SOC2								
	PT21							
	PT22							
	...							
...								

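### The optional AE summary tables (SAP Tables 4.1-4.3) have no arm breakdown, although the safety objective is stated by arm

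*SAP*

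**What the plan says.** The SAP's secondary objectives (section 3.4) include "Safety profile according to the National Cancer Institute's (NCI) Common Terminology Criteria of Adverse Events (CTCAE) version 5.0 criteria in experimental and control arms". Protocol 3.2.2 and 10.1 also state safety by arm. The reduced SAP drops some secondary objectives in section 4.3.6, but that section excludes safety.

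SAP 4.3.9 places all AEs in Listings 28.1 and 28.2 and then adds a conditional step: "Optionally, if the number of AEs is sufficient, then the AEs will be analyzed in frequency tables". The mock-ups in SAP 5.1 lay these tables out as follows:

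- Table 4.1 (overview): columns for 5-FU, folinic acid, irinotecan, cetuximab and Total. The folinic acid header begins "Folinic acid [N".
- Table 4.2 (events by system organ class and preferred term): columns for CTCAE grades 1 to 5 and Total.
- Table 4.3 (patients by maximal grade): the same column structure, with a top row "Number of patients with any AE".

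The other tables in the same section do show arm. Table 1 has a block "Number of patients in treatment arms", Table 2 has rows A, B and Total, and Table 3 has columns Arm A, Arm B and Total.

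**The concern.** A summary table of harms in a two-arm trial normally shows the arms, and here the objective asks for that. The three AE tables are the only planned aggregate presentation of safety. If they are filled in as drawn, a reader of the summary could not tell whether events occurred with the cetuximab switch strategy or with FOLFIRI alone. Table 4.1 adds a risk of misreading. Its drug columns have no definition in the available text, so the cetuximab column could be taken for Arm A when it may mean something else.

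**Working it through.** The plan gives no figure to reproduce. The check compares the layouts with the objective.

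| Output in SAP 5 | Content | Arm shown? |
|---|---|---|
| Table 1 | Patient counts | Yes (counts only) |
| Table 2 | Time to first RAS wild-type | Yes (rows) |
| Table 3 | Response | Yes (columns) |
| Table 4.1 | AE overview | No (drug columns) |
| Table 4.2 | Events by SOC/PT and grade | No (grade columns) |
| Table 4.3 | Patients by SOC/PT and maximal grade | No (grade columns) |
| Listings 28.1, 28.2 | AEs by patient | Yes |

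Arm is shown in 0 of 3 AE tables, and in both of the other tables that report a result (Tables 2 and 3). Table 1 supplies only the denominators by arm.

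**Repetition by arm.** The text of SAP 4.3.9 and the table list in SAP 10 do not say that the AE tables are produced once per arm.

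**Drug columns as a substitute for arm.** There are two possible readings of Table 4.1.

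1. *Exposure.* Protocol 5.1 gives irinotecan, folinic acid and infusional 5-FU in both arms, so those columns would largely repeat Total. The cetuximab column would match Arm A only if it meant ever exposed and every Arm A patient in the mITT set had received cetuximab. The mITT definition does not ensure this: "All randomized patients who received at least 1 dose, complete or incomplete, of study medication". The protocol's schedule of assessments also counts FOLFIRI before randomisation as study treatment. If the column meant current exposure, it would leave out Arm A periods after a switch back to FOLFIRI.
2. *Attributed causality.* Protocol 10.3 lists AE causality among the safety analyses, and Listing 28.1 collects causality for the same four drugs. On this reading the columns show which drug was suspected, not which arm the patient was in. The row for the number of patients in mITT would then have no clear meaning by drug.

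Neither reading gives an Arm A against Arm B summary. Some programmer text may not have survived in the extracted mock-ups, but SAP 5 says that such text would "show the programmer where the parameter to be analyzed may be found and will not appear in the report". It would not explain the columns to a reader of the report.

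**Which events are counted.** Protocol 10.1.2 defines the safety variable as all SAEs, plus those non-serious AEs that are treatment-related or lead to permanent discontinuation, "recorded from the date of signature of Informed Consent". Protocol section 9 has investigators report all AEs. Table 4.1 counts any AE without saying which definition applies.

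**Time before the arms differ.** Randomisation is at week 8 or 16 from the start of FOLFIRI (SAP 4.3.2).

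- 8 x 7 = 56 days; 56 / 14 = 4 planned cycles.
- 16 x 7 = 112 days; 112 / 14 = 8 planned cycles.
- Maximum treatment at the SAP's 30.4 days per month: 36 x 30.4 = 1094.4 days.
- 56 / 1094.4 = 5.1%; 112 / 1094.4 = 10.2%.

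These shares apply to a patient treated for the full 36 months. They would be larger with shorter treatment, but the documents do not give actual durations.

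**Scale.** Seven patients were enlisted (SAP 4.2), so one patient is at least 1 / 7 = 14.3% of any total.

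**The case against.** The strongest reply is that SAP 4.3.9 assigns safety to the listings, every listing carries arm (SAP 4.2 and 4.3.2), and the tables are a conditional extra. SAP 4.23 also discloses that most analyses are shown as listings. Protocol 10.3 does not ask for the safety summaries by arm, and the drug columns may well be there to report causality. With seven patients, the layout is then largely a matter of preference.

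Much of this stands. It limits the weight of the point, and it means that no written requirement for these particular tables is broken. It does not explain why safety, which is stated by arm, should be the one set of results summarised without arm when response and time to conversion are split at the same sample size. A causality purpose would justify a separate, labelled table rather than replacing the arms.

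A second reply is that including events from before randomisation follows the plan, which records safety from consent. That is correct. A reader might infer that this pooling is an error, but the documents call for it and nowhere require a split at randomisation. Adding arm columns would not change it either.

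There is also a caution about the text. After a page break, the lower rows of Table 4.1 carry more empty cells than its header has columns. This is probably an extraction artefact, and no arm label is visible anywhere in the table.

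**Conclusion.** The point holds as a minor reporting gap. If Tables 4.1 to 4.3 are produced as drawn, they will pool the arms and will not summarise safety in the way SAP 3.4 states the objective. A reader might go further and infer that safety by arm cannot be recovered. The documents do not support that, because Listings 28.1 and 28.2 give the randomised arm for each AE and the comparison can be rebuilt by hand.

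The consequence is descriptive only. No test, estimate or stopping decision rests on these tables, and the whole trial has seven enlisted patients. The conclusion assumes that the table headers in the available text are complete and that the option to produce the tables is taken up. If it is not, the listings already cover the objective at patient level.

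**What to change.** If the tables are produced:

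- Give Table 4.1 Arm A, Arm B and Total columns, as Table 3 already does, in the mITT/safety population.
- Present Tables 4.2 and 4.3 for each arm and in total.
- If by-drug causality is wanted, put it in a separate table headed as attributed causality, or leave it to Listing 28.1.
- Count events as protocol 10.1.2 defines the safety variable. If all AEs are shown instead, say so in the title or a footnote.
- Optionally, show events with onset on or after randomisation separately, because treatment is the same in both arms before then. In that case keep undated events in the overall count only and footnote their number, which is consistent with the no-imputation rule in SAP 4.4.

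The cost is a small mock-up and programming change. Arm and AE start date are already in Listings 28.1 and 28.2, and the randomisation date is in Listing 3. No new data, population or missing-data rule is needed.

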**(Optionally) Table 4.2: AEs - System Organ Class (SOC) and Preferred Term (PT) by NCI CTCAE grade**

SOC	PT	NCI CTCAE grade					Total	
		1	2	3	4	5	N	%
Number of AEs								100

SOC1								
	PT11							
	PT12							
	...							
SOC2								
	PT21							
	PT22							
	...							
...								

**(Optionally) Table 4.3: AEs - number of patients with respect to System Organ Class (SOC) and Preferred Term (PT) by maximal NCI CTCAE grade**

SOC	PT	Maximal NCI CTCAE grade					Total	
		1	2	3	4	5	N	%
Number of patients with any AE								100
SOC1								
	PT11							
	PT12							
	...							
SOC2								
	PT21							
	PT22							
	...							
...								

## 5.2 Listings

### Eligibility criteria:

#### **Listing 1.1: Inclusion criteria - legend**

Abbreviation	Full text
IC 01	Histologically confirmed, UICC stage IV adenocarcinoma of the left-sided colon or rectum with metastases, primarily non-resectable, confirmed RAS mutations proven in the primary tumor or metastasis (KRAS and NRAS exon 2, 3, 4)
IC 02	Age $\geq$ 18 years on day of signing informed consent
IC 03	No previous chemotherapy for metastatic disease (1-2 cycles FOLFIRI or mFOLFIRI are permitted before enrollment until RAS status is determined)
IC 04	Patient is suitable for chemotherapy administration
IC 05	ECOG performance status 0-1
IC 06	Consent to liquid biopsy and mutation analysis
IC 07	Estimated life expectancy $>$ 3 months
IC 08	Presence of at least one measurable reference lesion according to the RECIST v 1.1 criteria (chest CT and abdominal CT four weeks or less before enrollment)
IC 09	Adequate bone marrow function defined as: Leukocytes $3.0 \times 10^9/L$ with neutrophils $1.5 \times 10^9/L$ , thrombocytes $100 \times 10^9/L$ , and hemoglobin 9 g/dL
IC 10	Adequate hepatic function defined as: Serum bilirubin $1.5 \times$ ULN, ALAT, and ASAT $2.5 \times$ ULN (in the presence of hepatic metastases, ALAT and ASAT $5 \times$ ULN)
IC 11	Adequate renal function defined as: Creatinine clearance $\geq 50$ mL/min
IC 12	Adequate cardiac function defined as: Normal ECG and echocardiogram with a LVEF of 55%
IC 13	INR $< 1.5$ and activated PTT (aPTT) $< 1.5 \times$ ULN (patients without anticoagulation). Therapeutic anticoagulation is allowed if INR and aPTT have remained stable within the therapeutic range for at least two weeks
IC 14	Time interval of at least six months since last administration of any previous neoadjuvant/adjuvant chemotherapy or radio chemotherapy of the primary tumor in curative treatment intention to start of first-line treatment
IC 15	Any relevant toxicities of prior treatments must have resolved to grade $\leq 1$ according to the CTCAE (version 5), except alopecia
IC 16	WOCBP should have a negative urine pregnancy test within 72 hours prior to receiving the first dose of study medication
IC 17	Highly effective contraception for both male and female patients throughout the study and for at least three months after last dose of study medication administration if the risk of conception exists. Highly effective contraception must be in line with the definition of the CTFG recommendation
IC 18	Signed written informed consent and capacity to understand the informed consent
IC 19	Date of signing written informed consent

**Listing 1.2: Inclusion criteria 01-09**

patient.patient_no	registration.registration_arm_randomized	patient.patient_ic_01	patient.patient_ic_02	patient.patient_ic_03	patient.patient_ic_04	patient.patient_ic_05	patient.patient_ic_06	patient.patient_ic_07	patient.patient_ic_08	patient.patient_ic_09
Patient No.	Arm	IC 01 [yes/no]	IC 02 [yes/no]	IC 03 [yes/no]	IC 04 [yes/no]	IC 05 [yes/no]	IC 06 [yes/no]	IC 07 [yes/no]	IC 08 [yes/no]	IC 09 [yes/no]

**Listing 1.3: Inclusion criteria 10-19**

patient.patient_no	registration.registration_arm_randomized	patient.patient_ic_10	patient.patient_ic_11	patient.patient_ic_12	patient.patient_ic_13	patient.patient_ic_14	patient.patient_ic_15	patient.patient_ic_16	patient.patient_ic_17	patient.patient_ic_18	patient.patient_ic_ic_date
Patient No.	Arm	IC 10 [yes/no]	IC 11 [yes/no]	IC 12 [yes/no]	IC 13 [yes/no]	IC 14 [yes/no]	IC 15 [yes/no]	IC 16 [yes/no/na]	IC 17 [yes/no/na]	IC 18 [yes/no]	IC 19 [DDMMYY]

**Listing 2.1: Exclusion criteria - legend**

Abbreviation	Full text
EC 01	Right-sided mCRC
EC 02	Primarily resectable metastases
EC 03	Previous chemotherapy for the colorectal cancer except for adjuvant treatment, completed at least six months before entering the study (1-2 cycles FOLFIRI or mFOLFIRI are permitted before enrollment)
EC 04	Patients with known brain metastases
EC 05	Symptomatic peritoneal carcinosis
EC 06	Progressive disease before randomization
EC 07	History of acute or subacute intestinal occlusion, inflammatory bowel disease, immune colitis, or chronic diarrhea
EC 08	Grade II heart failure (NYHA classification), Myocardial infarction, balloon angioplasty (PTCA) with or without stenting, and cerebral vascular accident/stroke within the past twelve months before enrollment, unstable angina pectoris, serious cardiac arrhythmia according to investigator's judgment requiring medication
EC 09	Medical or psychological impairments associated with restricted ability to give consent or not allowing conduct of study
EC 10	Active infection with hepatitis B or C
EC 11	Additional cancer; exceptions include adequately treated basal cell carcinoma of the skin, squamous cell carcinoma of the skin, or in situ cervical cancer that has undergone potentially curative therapy without evidence of recurrence
EC 12	Uncontrolled hypertension
EC 13	Marked proteinuria (nephrotic syndrome)
EC 14	Arterial thromboembolism or severe hemorrhage within six months prior to randomization (with exception of tumor bleeding before tumor resection surgery)
EC 15	Hemorrhagic diathesis or tendency towards thrombosis
EC 16	Participation in a clinical study or experimental drug treatment within thirty days prior to study
EC 17	Known hypersensitivity or allergic reaction to any of the study medications
EC 18	Severe, non-healing wounds, ulcers, bone fractures, or an infection requiring systematic therapy
EC 19	Known history of alcohol or drug abuse
EC 20	Known complete DPD deficiency (phenotype and/or genotype test) (patients with partial DPD deficiency may be included in this clinical trial at the discretion of the investigator and should receive a reduced starting 5-FU dose); known glucuronidation deficiency (Gilbert's syndrome) (specific screening not required)
EC 21	Absent or restricted legal capacity
EC 22	For female patients only: Pregnancy (absence to be confirmed by $\beta$ -HCG test) or lactating

